[figure not shown]

#### 1.0 SPECIFIC STUDY AIMS

Specific Aim #1: To compare the accuracy and percent analytic agreement of clinicianand self-collected cervico-vaginal brush samples with Q-pad-collected menstrual blood for HR-HPV detection in HR-HPV positive women and women with no previous history of HR-HPV.

Specific Aim #2: 2.1: To assess the ability to detect oncoproteins in Q-pad collected menstrual blood samples from women with ASCUS+ to determine the utility in cervical cancer/precancer detection and 2.2: to test the utility of a low and high threshold HR-HPV reflex scheme to similarly increase the specificity of HR-HPV testing derived from menstrual blood.

# 2.0 BACKGROUND AND RATIONALE

Cervical cancer (CaCx) is the fourth most common cancer among women worldwide, and the 2nd highest cause of cancer-related mortality among women. Most cases of CaCx are preventable through the combination of screening and access to appropriate treatment of precancerous lesions. Papanicolaou (Pap) cytology screening has been the most widely applied screening method for cervical cancer or precancer but has variable sensitivity and specificity and, globally, cytology is not effectively available to women in developing countries (where 80% or all cervical cancers occur). The combination of variable test qualities and limited access results in continued high incidence of fatal cancers in many settings.

In recent years, tests to detect Human Papilloma Virus (HPV), particularly high-risk subtypes (HR-HPV) from cervical samples have been introduced in many settings and are poised to become a primary screening approach in the future. A known limitation to DNA-based HR-HPV testing is that it can only discriminate between presence or absence of an HPV specific DNA and cannot determine whether presence of the virus indicates mere infection or pre-cancer/cancer. Several studies have found that the molecular switch for the development of Cervical Intra-epithelial Neoplasia (dysplasia or CIN) and ultimately CaCx is the expression of the E6 and E7 onco-proteins resulting from infection with oncogenic HPV. Results demonstrates that the specificity of HR-HPV E6/E7 mRNA is higher than that of HR-HPV and that HR-HPV E6-E7 mRNA measured at baseline predicts future CIN2 or CIN3 development. Finally, it has been shown that compared with HR-HPV testing alone, HR-HPV/E6-E7 mRNA testing could reduce half of the colposcopy referrals generated by current prevention rubrics. Alternatively, changing the cycle threshold for a positive HR HPV test from low (high sensitivity) to high (high specificity) as a serial "reflex" test could have the same effect. In addition, the evolution to primary testing with HR-HPV has been accomplished in some settings using specimens obtained from patient self-collected swabs, obviating the need for the vast majority of women to undergo a gynecological exam, which is invasive, uncomfortable, and resource-intense.

Detection of HR-HPV with E6/E7 via self-collected samples could improve access to screening, improve sensitivity, and increase objectivity of testing. A variety of self-collection devices have been used to detect HPV including swabs, brushes, cervical

lavage devices, tampons, and urine. While most of these devices have comparable sensitivity for HR-HPV (compared to clinician collected samples), logistical challenges limit their utility. Most devices require instructions on proper insertion into the vagina (which can be culturally challenging in some settings), the specimens are difficult to transport, and often require storage in expensive, flammable fixative solution. A novel and innovative alternative involves the use of **menstrual blood** for the same diagnostic purpose. To this end, a specialized collection device integrated into an ordinary, inexpensive menstrual pad has been developed. Specifically, the "The Q-Pad" is a small, flexible, and easy-to-transport device involving dried paper – which essentially creates a Dried Blood Spot (DBS) specimen – embedded within a sanitary napkin. For purposes of CaCx screening, such a collection device does not require intra-vaginal manipulation of a brush/swab or lavage device and could improve participation in community screening efforts while also being easier to transport than urine or cervicovaginal samples. Menstrual blood has already been shown to corelate well with a number of commonly used serum tests such as Hemoglobin A1C and TSH.

Menstrual blood is composed of three distinct body fluids: whole blood, vaginal fluid, and endometrial cells shed from the endometrial lining. While menstrual blood has been presumed to be virtually identical to whole blood, important differences exist and have been understudied. Studies from the 1980s found that menstrual fluid lacks factor X, pro-thrombin, and free thrombin. Proteomic and small-scale HPV detection studies have been recently published on menstrual blood, yet rigorous, larger-scale and implementation-level studies remain to be performed. In preliminary (unpublished) findings on HR-HPV screening with the Q-pad, we found that device detected HR-HPV using the GeneXpert POC test, and, anecdotally, women preferred this approach to self-collected and clinician-collected samples. We found favorable participation in community-based screening. Additionally, in rural, low-resource settings, DBS is easier to transport than slides, urine, or liquid-based cervico-vaginal samples, requires no refrigeration, and can potentially provide a "woman's physical" in a self-collected sample.

Our proposed study would be the first to rigorously examine the utility and feasibility of using menstrual blood collected by women for detection of HR-HPV DNA and HPV E6/E7 mRNA, using the Q-pad. We hypothesize that using self-collected menstrual blood from the Q-pad may be a more convenient, comfortable and cost-effective method for HR-HPV and E6/E7 screening, compared to currently implemented approaches, with high correlation to conventional HR-HPV testing. Our approach to screening may also allow for improved access to screening for cancer and precancer in the areas with the highest burden of disease, including unscreened women in the US and worldwide.

#### 3.0 STUDY ENROLLMENT AND PARTICIPANT ELIGIBLITY

The participant population to be included in the study is menstruating women over the age of 18. There will be two groups: 1) menstruating women over the age of 18 who have a previous history of HR-HPV in the last 18 months and 2) menstruating women over the age of 18 who do not have a previous history of HR-HPV. We plan to recruit patients from Stanford research IT Starr cohort tool to identify patients who have had a positive

HR-HPV test in the past 18-months. In addition, we also plan to recruit women without previous history of HR-HPV, who present in clinic for a cervical cancer screening test as part of their standard of care well woman visit.

# 3.1 Study Enrollment

# For positive HR-HPV participants:

We plan to recruit patients from Stanford research IT Starr cohort tool to identify patients who have had a positive HR-HPV test in the last 18-months. We will then contact their provider to get permission to include them in the study before their next in-person follow up. This follow-up visit can be any time after positive HR-HPV result up to 18-months. This follow-up visit can be for a repeat cervical cancer screening pap test, colposcopy, or loop electrosurgical excision procedure. Patients identified who are HR-HPV positive will be contacted by their provider to broach the possibility of research participation to the patient. If this patient expresses interest in the project, the provider will ask if the research staff can then contact the patient. If the patient agrees, then the research staff will contact the patient. In addition, patient's with known positive HR-HPV results who present to the clinic for colposcopy or loop electrosurgical excision procedure will be approached by their provider during that clinic visit to see if the patient would be willing to participate in the project. If the patient agrees, then research staff will present the project in detail to the patient and obtain consent. Pre-procedure meetings (either in person or over the phone) will be performed with the subjects individually, where the process will be discussed and instructions on how to use the Q-pads and the vaginal swabs will be explained to ensure women fully understand the process. We will also hand out (or mail) instructions with pictures on paper to minimize any risk associated with using the devices. We do not anticipate any screen failures. Eligibility is based on standard of care testing.

# For participants with no prior HR-HPV history:

We plan to recruit patients from Stanford Gynecology clinic. We will review the clinic schedule for patients presenting to the clinic for their routine well woman visit with cervical cancer screening. Their provider will approach the patient during that clinic visit to assess if the patient would be willing to participate in the project. If the patient agrees, then research staff will present the project in detail to the patient and obtain consent. At the time of the routine cervical cancer screening, additional study swabs will be collected. Prior to discharge, research staff will show the subject how to use the Q-pads and the vaginal swabs to ensure subjects fully understand the process. We do not anticipate any screen failures.

# 3.2 Participant Criteria

The inclusion criteria are women older than 18 years, who regularly menstruate and have tested HR-HPV positive in the last 18-months. Further, we intend to include women older than 18 years who regularly menstruate and have not been tested HR-HPV positive in the last 18-months. The exclusion criteria are women younger than 18 years old or who are post-menopausal or not menstruating regularly.

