#### 3.3 Enrollment

The target number of subjects at our gynecology clinic is 250 patients with or without previous HR-HPV diagnoses. We expect to complete this study within 12 months.

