#### Provider sample collection

Participants will attend a scheduled, standard of care visit with their provider either for screening of HR-HPV or for follow-up within 18-months of the positive HR-HPV test for a repeat pap smear, colposcopy, or loop electrosurgical excision procedure. The provider will be asked to collect an additional sample for the study, which will be shipped to a laboratory for HR-HPV analysis. Additionally, at this time the participant will be asked to obtain two "self-swabs". While in clinic, she will be administered swab device kits with verbal and written instructions.

We are using a commercially available menstrual pad. The menstrual pad is made of organic cotton and is today commercially available in convenient stores such as CVS and Walgreens. The only difference to a normal product is a small strip that is embedded beneath the first cotton layer. The strip consists of medical grade materials manufactured according to the ISO 13495 standard for medical devices. The core material in the strip is a proprietary paper-based sample receiving material from GE, namely a Whatman 903 collection paper. This is a commercially available product.

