#### 5.2 Analysis plan

We will record all data on an electronic tablet using REDCap electric data capture tools hosted at the Stanford Center for Clinical Informatics. 25 IBM SPSS Statistics, version 25.0 (IBM Corp., Armonk, N.Y., USA) will be used for data analysis. We will assess sociodemographic and clinical characteristics using descriptive statistics; if comparisons are needed, chi square tests or Mann-Whitney U tests will be used, where appropriate. We will assess the percent agreement of the binary outcome of HPV positive or negative on the menstrual blood sample analysis compared to the clinician swab and the self-swabs using Cohen's kappa.

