#### **IV. Inclusion/Exclusion Criteria**

Inclusion Criteria (From IRB approved protocol)	Yes	No	Supporting Documentation*
1. 18 years or older			
2. Menstruate regularly			
3. Comfortable using menstrual pads			
4. Comfortable using vaginal swabs			
5. Comfortable committing to using condoms from time of self-collection and provider collected sample			
Exclusion Criteria (From IRB approved protocol)			
1. Women younger than 18 years old			
2. Women who are post-menopausal or not menstruating regularly			

\*All subject files must include supporting documentation to confirm subject eligibility. The method of confirmation can include, but is not limited to, laboratory test results, radiology test results, subject self-report, and medical record review.

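### Does the 18-month look-back in section 3.2 leave some eligible women outside both study groups in a way that affects the analysis?

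*Combined protocol and SAP*

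**What the plan says.** Section 3.2 lists two kinds of eligible women: those with a positive HR-HPV test in the past 18 months, and those who "have not been tested HR-HPV positive in the last 18-months". Its exclusions concern only age and menstrual status.

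Elsewhere the second group carries no time limit:

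- Aim 1 (section 1.0) speaks of "detection in HR-HPV positive women and women with no previous history of HR-HPV".
- Section 3.0 sets the window for the first group and drops it for the second in the same sentence: "in the last 18 months and 2) menstruating women over the age of 18 who do not have a previous history of HR-HPV".
- The second heading in section 3.1 reads "For participants with no prior HR-HPV history".
- Section 5.1 describes the primary-outcome population by whether or not women had earlier positive results, again with no window.

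Section 3.3 sets a single target of "250 patients with or without previous HR-HPV diagnoses". Section 5.2 plans percent agreement and Cohen's kappa for the menstrual sample against the clinician swab and the self-swabs. It does not mention history groups. For descriptive characteristics it adds that "if comparisons are needed, chi square tests or Mann-Whitney U tests will be used, where appropriate".

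**The concern.** Having no positive test in 18 months is not the same as never having had one. A woman with an older positive meets 3.2, yet she is too late for the first group in 3.0 and has too much history for the second. Nothing in the exclusions or the Appendix A criteria removes her, since neither mentions HR-HPV history. Section 4.0 describes the provider visit as "either for screening of HR-HPV or for follow-up within 18-months of the positive HR-HPV test", so the time limit there applies to follow-up and not to screening.

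At stake would be the description of the Aim 1 population and any result shown by history group. If a table had a column for women without previous HR-HPV, the definition would decide whether such a woman belonged in it. A statement about never-positive women could then be untrue of some of them.

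**Working it through.** The plan gives no figure to reproduce on this point. The check is to classify women under each definition and then ask which planned estimate uses the classification.

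**Step 1. Classify five histories** (18 months counted as inside the window).

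| Last positive test | Section 3.2 | Section 3.0 | Section 5.1, read literally |
|---|---|---|---|
| Never | second group | group 2 | without |
| 12 months ago | first group | group 1 | with |
| 18 months ago | first group | group 1 | with |
| 24 months ago | second group | neither | with |
| 60 months ago | second group | neither | with |

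The definitions agree except for women whose last positive was more than 18 months ago. For them 3.0 has no place, and 3.2 and 5.1 sort them in opposite directions. Both 3.2 and 5.1 cover every history, so these women are eligible and lie within the primary-outcome population.

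**Step 2. Trace the label into the primary analysis.** For each comparison, every woman falls in one cell of a two-by-two table of menstrual sample against swab. With cell counts a (both positive), b and c (discordant), d (both negative) and N their sum:

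- agreement: p_o = (a + d)/N
- chance agreement: p_e = [(a + b)(a + c) + (c + d)(b + d)]/N²
- kappa = (p_o − p_e)/(1 − p_e)

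Her cell depends on her two study results, not on an old test. Moving her from one history label to another leaves a, b, c, d and N unchanged, so agreement and kappa are unchanged too. Kappa does depend on the share of positives, so it could move if women were added or removed. But 3.2 already states who is eligible, and bringing the other sections into line with it removes nobody.

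**Step 3. Trace it into the secondary outcome.** The oncoprotein question concerns women with ASCUS+, which is a cytology finding. The threshold question concerns the assay. Neither uses the history groups.

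**Step 4. Ask how many women are involved.** Appendix B gives 70 women in the sample when the second group was added, against a goal of 250, so 250 − 70 = 180 places remained. That counts places, not women with an older positive. It does not bound the latter either: 3.1 also lets women with known positive results be approached at colposcopy or excision visits, in a sentence with no window. No useful size can be derived.

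**Step 5. Price the other way of settling the wording.** Narrowing 3.2 to women with no known positive would cost recruitment. If a share s of otherwise eligible women had an older positive, filling 180 places would need 180/(1 − s) willing women: 180/0.90 = 200 at s = 10%, and 180/0.70 ≈ 257 at s = 30%. Both shares are assumptions. These figures price that option and do not measure the slip.

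**The case for a change.** The best case for acting is that 3.2 is the section that states eligibility and it differs from every other description of the second group. Reading the absence of history as shorthand for everyone outside the first group is possible, but 3.0 writes the window for one group and omits it for the other in a single sentence. Staff guided by the 3.1 heading might pass over a woman with an older positive whom staff guided by 3.2 would enrol. Aligning the text and recording the date of her last known positive would be cheap.

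The textual part of this stands. The consequence is weaker:

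- Harm requires that such women were enrolled, that results were split by history although 5.2 plans no split, and that the label was applied without checking.
- The Appendix A list headed "Inclusion Criteria (From IRB approved protocol" assigns no woman to any group, so its silence says nothing particular about older positives.
- The visit wording in 4.0 concerns sample collection and does not establish a route of entry.
- The case-report fields are not shown and Appendix A asks for documents supporting eligibility, so her history may well be on file.

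**Conclusion.** The sections do not match, and an editor could tidy them, including 5.1. This is a clerical inconsistency and no change to the plan follows. Its effect on the planned pooled agreement and kappa is nil if the wording is settled in line with 3.2, because no woman enters or leaves the analysis and no cell of any table changes. The alternative of narrowing eligibility would cost recruitment, in a study whose Appendix B already reports that fewer women menstruate regularly than expected, and would buy nothing for the planned estimates.

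The conclusion rests on 5.2 being carried out as written, pooled over history. If the investigators later present results by history, a careful analyst would state the definition used and reserve a never-positive label for women with no known positive test. That is ordinary reporting practice. Which definition the sponsor prefers is for the sponsor to say; the documents do not settle it.

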#### 3.3 Enrollment

The target number of subjects at our gynecology clinic is 250 patients with or without previous HR-HPV diagnoses. We expect to complete this study within 12 months.

## 4.0 MATERIAL AND METHODS

#### Pre-procedure

Pre-procedure meetings will be performed with the subjects individually where the process will be discussed and two designated menstrual pads (pad 1 and pad 2) and two pouches (pouch 1 and pouch 2) will be dispensed. We will instruct the subjects on how to use the pads and go through the consent form with them and answer any questions they might have.

#### Self-Sample collection

Participants will use the pads as close to their scheduled, standard of care appointment or follow-up appointment —either during the menstrual cycle before or after the appointment. When the woman has her period, she uses the pads following instructions given to her orally and in written format during the pre-procedure meetings.

The Q-pad is used like any other menstrual pad. After usage you pull a small slip which removes a small paper-based collection strip. She will dispose the pad and put the collection strip into the provided envelope.

The strip will be put in a pre-stamped envelope and into a mailbox and shipped to a CLIA waived and CAP certified laboratory for analysis. Results will be emailed back to the investigators in a coded fashion. DNA will not be extracted from the samples and the Stanford Tissue Bank will not be used for the banking of specimens. Samples will be disposed of after completion of the current study.

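### A loop excision can fall between the swabs and the Q-pad sample, and section 5.2 has no rule for such pairs, so a true change in HPV status could be counted as Q-pad disagreement

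*Combined protocol and SAP*

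**What the plan says.** Section 4.0 (Provider sample collection) places the comparator samples at a standard-of-care visit, either for screening or "for follow-up within 18-months of the positive HR-HPV test for a repeat pap smear, colposcopy, or loop electrosurgical excision procedure". At that visit "The provider will be asked to collect an additional sample for the study", and the self-collected comparator belongs to the same visit: "Additionally, at this time the participant will be asked to obtain two" self-swabs. Whether these are taken before or after a procedure done that day is not stated.

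Section 4.0 (Self-Sample collection) lets the pads be used "either during the menstrual cycle before or after the appointment". The same sentence asks for use near the appointment but gives no limit in days.

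Section 3.1 adds a recruitment route: women with known positive results "who present to the clinic for colposcopy or loop electrosurgical excision procedure will be approached by their provider during that clinic visit". A woman first approached at that visit can use the pads only afterwards.

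Section 5.2 assesses agreement of the binary HPV result "on the menstrual blood sample analysis compared to the clinician swab and the self-swabs" with Cohen's kappa. It defines no analysis set and says nothing about sample order, interval or a procedure between samples. The exclusions in section 3.2 concern age and menstruation only. Appendix A has one item on the period around sampling: "Comfortable committing to using condoms from time of self-collection and provider collected sample".

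**The concern.** The primary outcome in section 5.1 is the accuracy and agreement of the Q-pad against the swabs. That comparison measures the device only if both samples reflect the same infection status. The condom item shows that the plan already guards the interval against new exposure; nothing comparable covers treatment.

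If an excision lies between the samples and status changes with it, a pad that reads correctly on its own day is scored as wrong. With swabs first and pad later, the discordance is swab-positive, pad-negative, and positive agreement falls. With pad first and swabs later, it is swab-negative, pad-positive, and negative agreement falls. Because this error is systematic, a larger sample would not remove it. Excision visits arise only among women with a positive HR-HPV history, the group likely to supply most of the information on positive agreement.

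**Working it through.** **Which orderings separate a pair**

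| Order | Excision between samples? |
|---|---|
| swabs, excision, pad | yes |
| pad, excision, swabs | yes |
| excision, swabs, pad | no, both after |
| pad, swabs, excision | no, both before |

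The documents permit all four and give no frequencies. For a woman first approached at the excision visit, only the first and third are possible.

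**The plan's own figure.** Section 5.3: 10,000 visits × 5% prevalence × 50% recruitment = 250, which reproduces. The point does not depend on this figure; 250 serves only as the denominator below.

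**Assumed inputs (none is in the documents).** 30% clinician-positive (75 of 250), positive agreement 90%, negative agreement 95%. Let f be the share of clinician-positive women whose excision falls after the swabs and before the pad, and c the share of those whose infection has cleared by the pad sample. Cleared women read pad-positive 5% of the time.

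**Base case.** Observed agreement = 0.30×0.90 + 0.70×0.95 = 0.935. Pad-positive share = 0.27 + 0.035 = 0.305. Chance agreement = 0.30×0.305 + 0.70×0.695 = 0.578. Kappa = (0.935 − 0.578)/(1 − 0.578) = 0.846. The 95% half-width is 1.96 × √(0.935×0.065/250)/0.422 = 0.072.

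**Swabs before excision, pad after.** Positive agreement = 0.90 − (0.90 − 0.05)·f·c = 0.90 − 0.85·f·c. Extra misses = 75 × 0.85·f·c. Overall agreement = 0.935 − 0.30×0.85·f·c.

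| f | c | Positive agreement | Overall agreement | Extra misses | Kappa | Loss |
|---|---|---|---|---|---|---|
| any | 0 | 90.0% | 93.5% | 0 | 0.846 | 0 |
| 5% | 20% | 89.2% | 93.2% | 0.6 | 0.840 | 0.006 |
| 10% | 20% | 88.3% | 93.0% | 1.3 | 0.833 | 0.013 |
| 5% | 50% | 87.9% | 92.9% | 1.6 | 0.830 | 0.016 |
| 10% | 50% | 85.8% | 92.2% | 3.2 | 0.814 | 0.032 |
| 20% | 70% (extreme) | 78.1% | 89.9% | 8.9 | 0.753 | 0.093 |

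Varying the clinician-positive share from 15% to 50%, the loss for f=10%, c=50% runs from 0.027 to 0.043, and for the extreme row from 0.078 to 0.119. At 50% positive the half-width is 1.96 × √(0.925×0.075/250)/0.5 = 0.065, so 0.043 is still inside it.

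**Pad before excision, swabs after.** Here f is the share of the 30% truly positive at the pad sample whose swabs follow an excision, and c the share cleared by the swabs. With f=10%, c=50%, 0.30×0.05 = 0.015 of women become swab-negative. Negative agreement = 1 − (0.70×0.05 + 0.015×0.90)/0.715 = 93.2%, and kappa is 0.815. Positive agreement stays at 90%.

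**The case against.** The strongest reply is that the harm needs a premise the documents do not contain: nowhere do they say that excision clears HR-HPV, or that it does so by the next menses. That stands. A reader might infer that kappa must fall for these women, but it falls only if c is above zero, and at c=0 nothing happens.

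A reader might also infer that every woman seen for loop excision, or at least every woman recruited at that visit, gives a separated pair. The documents do not support this. If her swabs follow the procedure, swabs and pad are both post-excision and comparable. The request to use the pad near the appointment also works towards a short gap, although it is not a treatment rule and sets no limit.

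On size, the moderate scenarios cost 0.6 to 3.2 extra misses and move positive agreement by 0.9 to 4.3 points, against a half-width of 6.8 points with 75 positives. Only the extreme row exceeds sampling error, and nothing in the documents points to f=20% or c=70%. Loop excision is one of several visit types, and enrolment includes women attending routine screening with no HR-HPV history.

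Finally, sample dates and visit procedure can probably be recovered from records, so part of the question could be examined later. The order of swabs and excision within a visit may not be recoverable, and an analysis set chosen after discordant pairs have been seen is open to challenge. That is the reason to settle the rule now.

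**Conclusion.** The gap is real and minor. Sections 3.1 and 4.0 allow an excision between the comparator and Q-pad samples in two of four orderings, and section 5.2 would pool those pairs with the rest. Under assumed moderate inputs (f of 5 to 10%, c of 20 to 50%, 30% clinician-positive, positive agreement 90%, negative agreement 95%) the kappa loss is about 0.01 to 0.03, below the half-width of about 0.07. It is zero if status does not change, and about 0.09 in an extreme case that the documents do not support.

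The stronger conclusion, that the primary agreement result will be materially biased against the Q-pad, does not follow. It would need the number of separated pairs, the swab order and the rate of change, and the documents give none of these. What can be said is that the plan as written could count a correct Q-pad result as disagreement and has no way to show whether it did.

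**What to change.** In REDCap, record the date of each sample, the visit procedure, and whether the clinician sample and the self-swabs were each taken before or after it.

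In section 5.2, pre-specify kappa with positive and negative percent agreement for two sets: all pairs, and pairs with no excision between the comparator and Q-pad samples. State in advance which is primary. Treat pairs of unknown order as possibly separated: leave them out of the unseparated set and keep them in the all-pairs set. Such pairs may already exist, since Appendix B mentions a sample of 70 at the time enrolment was widened. Report the separated pairs on their own.

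The cost is a few database fields and one analysis-set rule. Intervals widen slightly in the unseparated set. With f=10% there are 75 × 0.90 = 67.5 positives, and the positive-agreement half-width 1.96 × √(0.9×0.1/n) goes from 6.8 to 7.2 points; kappa's goes from 0.072 to 0.076. Removing positives also lowers prevalence, which alone moves kappa from 0.846 to 0.842. The unseparated set has a narrower disease spectrum because it holds fewer excision-treated women; the all-pairs result covers that. No change to clinical care is proposed.
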